4.1 Diet intervention

4.1.1 VLED phase (0-13 wks): A commercial micronutrient-replete VLED (3400 kJ (800 kcal)/day) will be provided (Optifast, Nestle Health Science) to replace normal meals along with ample fluids and low starch vegetables for 13 weeks. Participants will be required to add 1 teaspoon of olive oil daily (to assist with gall bladder contraction and thereby reduce the chance of biliary complications) and may add a psyllium husk based fibre supplement if constipation develops. Participants with a BMI >40 kg/m² will have an additional meal replacement product with the goal of preserving lean body mass during weight loss.

Participants will return for review one week after commencement of the VLED and at two weekly intervals thereafter until week 13 (total of 7 appointments) and the commencement of the food reintroduction stage.

To allow some flexibility for patients whose commitments vary, the VLED phase may be permitted to continue up to 21 weeks. Any patient whose BMI falls below 23 kg/m² before week 13 will be moved forward to the 'food reintroduction and weight maintenance' phase. Reasons for moving to food reintroduction before week 13 will be recorded.

Food Reintroduction phase (weeks 13-18):

A stepped transition to food-based Weight Maintenance in which the VLED will be gradually replaced with meals that contain 30% of energy from fat. During this phase participants will attend for review appointments every 2 weeks.

Week 13: step down to 2 Optifast meal replacement products per day + 1 low-fat meal/day + 2 servings of fruit, 1 serve low fat dairy and free (low starch) vegetables. Total intake 4200kJ (1000kcal)/day.

Week 15: step down to 1 Optifast meal replacement product per day + 2 low-fat meals/day + 2 servings of fruit, 2 serves low fat dairy and free vegetables. Total intake will 5000kJ (1200kcal)/day.

Week 17: 3 low-fat meals per day + 2 servings of fruit, 2-3 serves low fat dairy and free vegetables. Total intake 6000kJ (1400kcal)/day.

To allow flexibility for patients whose confidence varies, the food introduction phase will be permitted to be varied between the protocol-defined limits of 2-8 weeks before switching to full food-based weight maintenance. Reasons for moving to weight loss maintenance without completing food reintroduction will be recorded.

4.1.2 Weight Maintenance Phase (weeks 21-52):

Individuals will be provided with an individually tailored calorie prescription using a food units system to support weight stabilisation and prevent weight regain with monthly review appointments.

Maintenance Diet - low-fat healthy eating weight loss maintenance intervention [target below 30% energy from fat to a maximum of 35% energy from fat, flexibility is to optimise compliance].

Physical Activity - All subjects who are physically capable will be advised about increasing daily physical activity. As an aid, patients will be provided with a step-counter and recommended to aim to reach and maintain their individual sustainable maximum, with target of 15,000 steps/day.

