TDR	Total Diet Replacement
GIG	Governance and implementation Group

STUDY SYNOPSIS

[figure not shown]
Title of Study:	Diabetes REmission Clinical Trial-Aus; DiRECT-Aus
Study Centre:	University of Sydney
Duration of Study:	Active intervention: 12 month per subject Follow up: 4 years after completion of active intervention
Primary Objective:	
To determine whether a program, designed to achieve remission of T2DM to normal glucose tolerance by substantial weight loss using a very low energy diet (VLED), can be effectively delivered within the routine primary care setting where most people with T2DM are managed in Australia.
 
The Diabetes Remission Clinical Trial (DiRECT) was a study funded by Diabetes UK that tested whether a low calorie-based weight management program, delivered in primary care could result in long term Type 2 diabetes remission. Diabetes UK, the University of Glasgow and Newcastle University have since developed the DiRECT principles, which set out the core elements of health intervention to have the best chance of replicating the outcomes of the DiRECT study.
 
This project intent is to replicate or better the remission results achieved in the UK DiRECT study for people with T2DM in the participating PHN regions and undertaking the intervention in general practice.

Secondary Objective:	To evaluate the attitudes of participants to the VLED program including acceptability, ease of use and perceived value.
Primary Endpoint:	% of participants achieving a non-diabetic HbA1c (<6.5%; <48 mmol/mol) at 12 months having ceased all diabetes medication for at least the preceding 2 months
Rationale:	Bariatric surgery can convert 70-80% of people with T2DM to the non-diabetic state. The DiRECT trial provided evidence that T2DM could also be reversed by a strict energy restricted diet, with 10-15kg weight loss. The present study will determine if the results of the DiRECT trial can be replicated in an Australian primary care setting and establish whether it is possible to produce remission of T2DM at 12 months and sustain it over 5 years. An VLED can be provided relatively cheaply in the primary care setting where obesity and T2DM are managed, using a total diet replacement (TDR), such as Optifast, which is readily available to the Australian general public. The study will also assess quality of life and attitudes of subjects during the intervention.

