4.3.1 Height

Height will be measured to the nearest mm, using a stadiometer. Height will be measured at screening and Appt 20 (Week 52). Measurements will be taken in socks, stockings or bare feet. The patient is to stand with their back to the wall, feet together and heels touching the wall and feet flat on the ground with the head held horizontal.

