4.3.2 Body weight

Body weight will be measured to the nearest 100g in light clothing without shoes using approved calibrated scales. The scale will be placed on a hard, flat surface. Weight will be measured at all appointments.

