5. ASSESSMENT OF SAFETY

Given the nature of the intervention there is very low likelihood of safety concerns. Patients will be closely monitored throughout the study with review appointments 2 weekly during the VLED and Food Reintroduction phases of the study and then monthly until week 52.

At each appointment blood pressure and postural hypotension will be monitored and antihypertensive therapy reduced, withdrawn or reintroduced if necessary, by the GP as described in section 4.2.2. Similarly, glycaemia will be monitored throughout the study as described in section 4.2.2 and appropriate treatment provided by the GP.

Any observations/results which may pose a risk to health will be discussed with the patient and their GP.

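### The BMI <23 rule for leaving the VLED stops at week 13, although the VLED may run to week 21

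*Protocol*

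**What the plan says.** Section 4.1.1 prescribes the VLED for 13 weeks and then relaxes that: "To allow some flexibility for patients whose commitments vary, the VLED phase may be permitted to continue up to 21 weeks". The next sentence gives the low-BMI rule: "Any patient whose BMI falls below 23 kg/m² before week 13 will be moved forward" to the food reintroduction and maintenance phase. The sentence after it carries the same time limit: "Reasons for moving to food reintroduction before week 13 will be recorded".

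On oversight, Section 5 provides for "review appointments 2 weekly during the VLED and Food Reintroduction phases of the study", and states that findings posing a risk to health are discussed with the patient and the GP. Section 4.3.2 says "Weight will be measured at all appointments". Section 4.3.1 has height taken at screening and at week 52. Section 10 says that changes in phase length within the Section 4 limits need no amendment.

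**The concern.** The extension and the BMI rule stand in adjacent sentences but cover different periods. Before week 13 the protocol leaves no choice: below BMI 23, the participant moves on. From week 13, a participant who is allowed to continue is on the same 800 kcal/day diet after a longer period of restriction, and the rule no longer applies. Whether that participant stops below BMI 23 then depends on the judgement of the practice. The intervention is delivered by nurses or dietitians in many practices, so that judgement may differ from one to another.

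At stake are participant safety and a consistent definition of the intervention. The remission endpoint, its analysis and the sample size are not touched.

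**Working it through.** **1. Is there a BMI limit anywhere for weeks 13 to 21?** The uses of BMI in the protocol text available are:

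| Place | Use of BMI | Exit rule for an extended VLED? |
|---|---|---|
| Synopsis, Section 3.2 | Entry, BMI >27 | No |
| Section 3.4.1 | Comparison with non-participants | No |
| Section 4.1.1 | Extra product if BMI >40 | No |
| Section 4.1.1 | Move on if BMI <23, before week 13 | No, ends at week 13 |
| Section 1 | Background | No |

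Section 5 gives a general duty to discuss health risks, without a BMI threshold or a required change to the diet. The rescue plans in Section 4.1.3 concern weight regain or return of diabetes.

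**2. Length of the uncovered period.** 21 − 13 = 8 weeks at most, which is 8/13 = 62% on top of the standard phase.

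**3. An illustration.** Take a participant at BMI 23.4 at week 13 who is allowed to continue. Reaching 23 needs a further 0.4 × height². That is 0.4 × 2.56 = 1.0 kg at 1.60 m, 0.4 × 2.89 = 1.2 kg at 1.70 m, and 0.4 × 3.24 = 1.3 kg at 1.80 m. No rule is triggered when it happens.

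**4. Who could come near BMI 23?** The entry limit is BMI >27 (Section 3.2). The Synopsis rationale says that "T2DM could also be reversed by a strict energy restricted diet, with 10-15kg weight loss", with no time point. The heights are assumptions.

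- Loss needed (kg) = (entry BMI − 23) × height².
- Highest entry BMI that reaches 23 with a loss of L kg = 23 + L/height².

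| Height (assumed) | Loss needed, BMI 27 to 23 | Loss needed, BMI 30 to 23 | Highest entry BMI, 10 kg loss | Highest entry BMI, 15 kg loss |
|---|---|---|---|---|
| 1.60 m | 4 × 2.56 = 10.2 kg | 7 × 2.56 = 17.9 kg | 23 + 10/2.56 = 26.9 | 23 + 15/2.56 = 28.9 |
| 1.70 m | 4 × 2.89 = 11.6 kg | 7 × 2.89 = 20.2 kg | 23 + 10/2.89 = 26.5 | 23 + 15/2.89 = 28.2 |
| 1.80 m | 4 × 3.24 = 13.0 kg | 7 × 3.24 = 22.7 kg | 23 + 10/3.24 = 26.1 | 23 + 15/3.24 = 27.6 |

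A 10 kg loss takes no eligible participant below 23, since every value in that column is under the entry limit. A 15 kg loss does so only for entry BMI up to 27.6 to 28.9. From BMI 30 the loss needed lies beyond the cited range.

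**5. What cannot be computed.** The protocol gives neither a BMI distribution at week 13 nor a frequency of extension, so the share affected cannot be derived. Section 1.1 quotes a loss of 10.0 kg (SD 8.0) in the UK intervention arm, so losses of 10 to 13 kg are not exceptional. That figure says nothing about who would be extended or who would cross 23 after week 13.

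**The case against.** The strongest reply is that the rule is needed only where continuing is automatic. Up to week 13 the diet goes on by default, so a forced exit makes sense. After week 13 the default is to stop, and someone has to permit the extension, so a lean participant leaves unless a clinician decides otherwise. The extension is offered to people whose commitments vary, who may have had a delayed or interrupted diet and need not be the ones nearing BMI 23. Review stays two-weekly, weight is taken each time, the GP is available, and the adverse event form allows study treatment to be modified or stopped. The protocol also gives no reason for the figure 23, so calling it a safety limit is an inference.

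Much of this stands, and it is why the point is minor. Eight weeks is an upper bound, monitoring continues, and several conditions must coincide before anyone is affected. But the permission to extend carries no BMI condition, and monitoring without an action limit is not an exit rule. Whatever the purpose of 23, the protocol treats it as a point where the VLED must end, and nothing in it explains why that should hold at week 11 and not at week 15.

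**Conclusion.** The concern holds as a minor point. Followed to the letter, the protocol lets a participant below BMI 23 remain on the 800 kcal/day diet for up to 8 further weeks. The reading of the text is firm. The practical size is small and cannot be estimated. On the 10 to 15 kg figure and assumed heights of 1.60 to 1.80 m, it concerns mainly participants entering at about BMI 27 to 29, and of those only the ones who are extended and first fall below 23 after week 13. Regarding this as a safety matter rests on the assumption that the threshold is meant to protect participants.

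**What to change.** In Section 4.1.1, replace the limit to the period before week 13 in the BMI rule with: at any time while on the VLED, including any extension to week 21. Change the sentence on recording reasons to match, so that an extended VLED ended by this rule is also documented.

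No new measurement is needed, because screening height and the weight at each appointment give the BMI. Appendix A lists weights at weeks 15, 17 and 21 but no week 19 visit, so two-weekly checks throughout an extension rest on Section 5.

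The cost is one changed phrase and one recorded reason. A few participants would leave an extended VLED earlier than they otherwise might.

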4.1.3 Rescue Package for weight regain or re-emergence of diabetes

Many patients find weight maintenance difficult. Some patients relapse temporarily and gain weight rapidly and others may let things slip more gradually. Pilot studies showed the value of a sympathetic, but firm approach to relapse/regain management.

If weight regain occurs or if diabetes is found to have returned (HbA1c > 48 mmol/mol [6.5%]) at any time during the weight loss maintenance stage, 'rescue plans' for weight gain prevention will be offered:

- 1) **Weight regain of >2 and up to 4kg:** offer the use of Optifast to replace one main-meal per day for 4 weeks.
- 2) **Weight gain of >4kg or re-emergence of diabetes at any time:** offer 4 weeks VLED with fortnightly practice nurse/dietitian review and then a 2-4 weeks food re-introduction (adding 1 meal/week as before). Low-fat dietary advice and physical activity will be reinforced for weight maintenance.

4.2 Medications

4.2.1 Recording of medications

All medications will be recorded at screening on a CRF with information on start and stop date, dose, route, frequency and indication. The indication must match a medical history term or adverse event term. Participants will be prompted regarding changes to medications at each visit (including start date, stop date & dose changes). Changes will be recorded on the medications CRF.

4.2.2 Management of blood glucose lowering and blood pressure lowering medications

Hypoglycaemic agents will be withdrawn on commencement of the VLED. Patients will be educated on detecting deteriorating glycaemia and glycaemia will be measured at each visit using capillary blood glucose measurement. HbA1c will also be measured 3-monthly. If capillary blood glucose is >15mmol/L or HbA1c >9% or >1% change in HbA1c from previous measurement, the GP will consider re-introducing oral hypoglycaemic medication. Recommencement of medication due to elevated blood glucose will be captured in the medication log and the reason noted.

Hyperglycaemia will also be recorded as an adverse event (see section 5).

Blood pressure will be measured at each visit during the first 12 months of the study. Subjects will be asked about symptoms of postural hypotension. If blood pressure is <110/60 mmHg, blood pressure medication will be reviewed and the medication will either be withdrawn or the dose reduced. If blood pressure is >140/90, prescription of blood pressure lowering medication will be considered by the GP.

All changes to blood glucose lowering and blood pressure lowering medications will be recorded on the medications CRF.

Other medications will be maintained, and their continued need and dosage reviewed as part of routine care.

4.3 Study assessments

Anthropometric and laboratory measurements will be collected throughout the study to assess eligibility, safety and efficacy. The procedure for these measurements is described below and the timing of these measurements is detailed in the study schedule (Section 4.6).

4.3.1 Height

Height will be measured to the nearest mm, using a stadiometer. Height will be measured at screening and Appt 20 (Week 52). Measurements will be taken in socks, stockings or bare feet. The patient is to stand with their back to the wall, feet together and heels touching the wall and feet flat on the ground with the head held horizontal.

4.3.2 Body weight

Body weight will be measured to the nearest 100g in light clothing without shoes using approved calibrated scales. The scale will be placed on a hard, flat surface. Weight will be measured at all appointments.

4.3.3 Waist circumference

Waist circumference will be measured at the mid-point between the iliac crest and last rib and recorded to the nearest 0.5 cm. If the rib and hip are indiscernible, girth is to be taken at the narrowest point. Measurements will be taken at the end of a normal expiration with the arms relaxed by the side and feet shoulder width apart. Two measurements will be taken and if measurements vary by >0.5cm, a third measurement is to be taken and the mean of the two nearest values recorded. Waist circumference will be measured at all appointments.

4.3.4 Hip circumference

Hip circumference will be measured at the widest point across the hips/buttocks area with patients standing tall, feet flat on the floor, arms comfortably to the side and bulky clothing removed, if possible. The tape will be placed horizontal to the floor but. Two measurements will be taken and if measurements vary by > 0.5cm a third measurement will be taken and the mean of the two nearest values recorded to the nearest 0.5cm. Hip circumference will be measured at screening and Appt 20 (Week 52)

4.3.5 Blood pressure –

Blood pressure will be measured while seated after 5 minute rest using either a stethoscope and sphygmomanometer or digital sphygmomanometer. The same type of equipment should be used for each participant for the duration of the study. The arm should be relaxed and resting on a table

or desk so that the participant is not supporting their own arm. The appropriate cuff size must be used to ensure accurate measurements. The upper arm should be encircled by at least 80% of the total length of the cuff. The cuff is to be applied around the upper arm so that the midpoint of the length of the cuff lies over the brachial artery and mid-height of the cuff is at heart level. The bottom of the cuff should be approximately 2 cm above the elbow crease. If measuring blood pressure manually, stethoscope will be placed over brachial artery and the cuff inflated to 160mmHg (in those with no history of hypertension) or 200mmHg (for those with a history of hypertension) and slowly deflated at 2-3mmHg. The first Korotkoff sound will be recorded for systolic blood pressure and the last Korotkoff sound will be recorded for diastolic blood pressure. Three recordings will be collected 2-3 minutes apart. The same arm will be used to measure blood pressure throughout the study. Patients will be asked about symptoms of postural hypotension and blood pressure will be measured at all appointments.

4.3.6 Capillary blood glucose measurement

Capillary blood glucose measurement will be performed by the researcher or by the patient witnessed by the researcher. The glucose test strip will be prepared by inserting into a meter without touching the sensor tip and the lancing device will be primed to no more than 2.0mmprick. Prior to measurement, the hands will be washed with warm water and soap and dried thoroughly and the arm dropped to the side to encourage blood flow. The edge of the finger will be pricked and after five seconds the blood droplet will be wiped away with the second droplet used for analysis. Downward pressure may need to be applied to assist with blood flow. Capillary blood glucose will be measured at all appointments.

4.3.7 Physical activity

Physical activity will be measured by step count using a mobile phone app of the patient's preference and the Baecke Physical activity questionnaire. If the patient does not have a phone with pedometer function physical activity will be measured by questionnaire alone. Average step count during two weeks will be recorded at Appt 2 (Baseline), Appt 9 (End of VLED) and Appt 20 (Week 52). The Baecke Physical Activity questionnaire will be administered electronically at the same appointments.

4.3.8 Questionnaires

Quality of Life (EQ-5D), Binge Eating and Food Acceptability Questionnaires will be administered electronically at Appt 2 (Baseline), Appt 9 (End of the VLED) and Appt 20 (Week 52).

Questionnaires will be self-completed at the end of the specific appointment.

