	
 • Myocardial infarction within previous 6 months • Learning difficulties which in the opinion of the investigator prevent the subject providing informed consent and complying safely with the diet • Use of weight loss agents or medications taken to primarily reduce weight (eg orlistat, lorcaserin, Qysmia, Contrave, GLP-1 receptor analogues, over the counter or herbal weight loss agents) within the past 3 months • Have ever been diagnosed with and eating disorder or engaged in purging behaviour • Pregnant/ considering pregnancy • people currently participating in another clinical research trial • Allergy to Optifast or any of its ingredients
Product, Dose, Modes of Administration:	
The intervention is a 3400kJ (800kcal)/day TDR, followed for 13 weeks, with stepped food reintroduction to long-term weight loss maintenance using a tested energy-restricted nutritionally balanced (30% fat, < 10% saturated fat) maintenance diet using food-group exchanges, and support for behaviour change. Physical activity will be encouraged with a recommendation of at least 30 minutes brisk-walking daily and aiming to reach and maintain an individual sustainable maximum with a target of 15,000 steps/day.
 
Participants will continue to receive standard care under current clinical guidelines for T2DM. Intention to treat analysis will be conducted, with follow-up data continuing to be collected even if treatment is stopped.
 
The intervention will be delivered in primary care practices by practice nurses/dietitians (according to local availability and practice) with training, support and mentoring from the Boden Collaboration, University of Sydney.

Duration of Treatment:	12 months. Subject to additional funding, at least annual follow up for 5 years
Statistical Analysis:	
Data will be analysed primarily on an intention-to-treat (ITT) basis, using last observation carried forward for weight and diabetes status for subjects who discontinue the formal weight management program or experience an adverse event.
 
A ‘completers analysis’ of participants who complete the study will also be performed.

STUDY FLOW CHART

Screening and Baseline appointments

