3.5 Withdrawal of subjects

Patients who withdraw from the study after commencement of participation in the study will continue to have data collected from their routine GP visits, unless they specifically withdraw consent for this. Data on weight and HbA1c recorded in GP notes within 3 months either side of the patients planned 12 months follow-up date will be used. Data analysis will use best available follow-up weights (from routine attendances) and end of study diabetes status for subjects who discontinue the formal weight management program.

Diet intolerance or poor-compliance will be recorded: these patients will be included in ITT analysis, but excluded in 'completers analyses'. The same procedures will be used to obtain the five year follow-up data.

4. Trial procedures

Practices will deliver an VLED phase followed by structured food reintroduction and long term weight loss maintenance. Training for the practice nurses/dietitians in VLED delivery, maintenance diet program and behaviour therapy will be provided by the Boden Collaboration, University of Sydney. Training for the practice nurses/dietitians in the maintenance diet program and behaviour therapy will be provided by Diabetes NSW & ACT. To increase access in regional areas, practices may deliver the intervention via telehealth but all participants will attend their GP practice for safety monitoring and collection of study data.

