4.5 Outcome measurements

• 4.5.1 Primary Outcome Measure

The study primary outcome measurements are:

- reversal of diabetes (HbA1c <6.5% (48mmol/mol), off treatment for at least 2 months at 1 year (52wks)

• 4.5.2 Secondary Outcome Measure

Change in:

- Weight
- Quality of Life measured by EQ-5D
- Impact of VLED on eating behaviours measured by Binge Eating Score,
- VLED acceptability measured by Food Acceptability Questionnaire
- Physical Activity measured by the Baecke physical activity questionnaire and where available step count

Serum Lipids

Change in medications

HbA1c

lipids

LFTs

Renal function

and questionnaire scores.

The remaining outcome measurements will be collected at baseline and repeated at Appt 9 (End of VLED) and Appt 20 (Week 52). Subject to funding, these measurements will be repeated at 2 years and then every 12 months up to 5 years.

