4.6 Study schedule

Eligibility for the study and reintroduction of blood glucose lowering and blood pressure lowering medication, if required, will be determined by the GP. All other aspects of the study appointments may be delegated to the study dietitian or nurse according to local preferences and where the study dietitian and/or nurse are willing and able to perform the procedures in the GP's opinion. The GP will be available for discussion and guidance if required by the study dietitian or nurse.

Appointment (Appt) 1 (Week -2): Screening

- Review and discuss study participation
- Secure informed consent
- Assign study ID,
- Eligibility check performed by GP
- Record medical history and medications
- Measurement of: height, weight, waist & hip circumference & blood pressure
- Provide request form for fasting blood test and urine test to be completed prior to the baseline visit: HbA1c, glucose, urea & electrolytes, creatinine, eGFR, CaPO₄, magnesium, liver function tests, lipids, full blood count and urine sample for albuminuria
- Perform Urine pregnancy test in women of childbearing potential
- Advise patient that two week step count monitoring will be collected at next visit

Appt 2 (Week 0) Baseline

- Collect 2 weeks record of daily steps
- Measurement of weight, waist circumference, blood pressure and capillary blood glucose (measured by blood glucose meter)
- Record any changes to medications
- Record any adverse events
- Hypoglycaemic medications discontinued. If capillary blood glucose > 15mmol/L the GP will determine what actions to be taken with hypoglycaemic medications.
- Antihypertensive medications reduced or ceased only if BP <110/60

- Commence VLED phase of intervention
- Questionnaire completion: EQ-5D, Binge Eating Disorder, Beacke Physical Activity and Food Acceptability Questionnaire
- Provide 1 week supply of Optifast and instructions for ordering Optifast

Appt 3-9 (Weeks 1-13): Continue VLED

- Measurement of weight, waist circumference & blood pressure
- Capillary blood glucose measured by blood glucose meter
- Record any changes to medications
- Record any adverse events
- Continue VLED intervention
- Check participant supply of Optifast

Appt 9 (Week 13) - Food reintroduction

- Begin structured food reintroduction (Step 1)
- Provide request form for non-fasting blood test to be completed within 2 days of appointment: HbA1c
- Measurement of weight, waist circumference & blood pressure

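### No acceptability questionnaire is planned when a participant stops the VLED early or withdraws, so the answer to the only secondary objective may be overstated

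*Protocol*

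**What the plan says.** The Study Synopsis gives a single secondary objective: "To evaluate the attitudes of participants to the VLED program including acceptability, ease of use and perceived value". Section 4.5.2 ties acceptability to one instrument: "VLED acceptability measured by Food Acceptability Questionnaire".

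Section 4.3.8 says that the questionnaires are "administered electronically at Appt 2 (Baseline), Appt 9 (End of the VLED) and Appt 20 (Week 52", and adds: "Questionnaires will be self-completed at the end of the specific appointment". The study schedule in Section 4.6 and the table in Appendix A show the same three time points. Section 4.6 also lists "Commence VLED phase of intervention" among the Appt 2 activities.

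On people who leave, three places matter:

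- The synopsis describes an intention-to-treat analysis "with follow-up data continuing to be collected even if treatment is stopped".
- Section 3.5 provides that, for patients who withdraw from the study, data from routine GP visits continue to be collected unless consent for this is withdrawn. What it names is "Data on weight and HbA1c recorded in GP notes", within a window around the planned 12-month date.
- Section 3.5 has diet intolerance and poor compliance recorded, and Section 4.1.1 has the reasons for an early move to food reintroduction recorded.

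No questionnaire is tied to stopping the VLED or to withdrawal anywhere in the protocol.

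**The concern.** A participant's view of the diet is informative only after some experience of it. The Appt 2 questionnaire is completed on the day the VLED starts, so it records expectation. The next one is at week 13 and requires attending Appt 9. Between the two there is no occasion on which someone who gives up is asked for a rating.

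People who give up may well be those who found the diet hardest to accept. If their ratings are missing more often than those of people who stay, the reported acceptability describes the stayers rather than everyone who started. That would bear on the one stated secondary objective and on the question in Section 1.2 of whether the model is acceptable in Australian primary care. It is a gap in data collection: an analysis plan can describe the missing answers but cannot recover ratings that were never requested. The remission endpoint is not affected.

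**Working it through.** The protocol states no figure on this point, so there is nothing to reproduce. The check sets the provisions side by side for each way of leaving, then shows how any bias would scale.

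**Who is due a rating after baseline**

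| Participant | Post-baseline questionnaire planned? | Basis |
|---|---|---|
| Completes the VLED and stays | Yes, weeks 13 and 52 | Section 4.3.8, Appendix A |
| Stops the VLED early, stays in the study | Yes, weeks 13 and 52, some time after stopping | Synopsis (follow-up continues); Section 4.3.8 does not limit the form to those on the diet |
| Withdraws from the study before Appt 9 | None | Section 3.5: routine GP data, naming weight and HbA1c |

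For the middle group the delay can be long. Someone who stops at Appt 3 (week 1) is next asked 13 − 1 = 12 weeks later, and then 52 − 1 = 51 weeks after stopping.

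For the last group, nothing else in the protocol supplies a rating. Last observation carried forward is specified for weight and diabetes status (synopsis and Section 6). Applied to this questionnaire, it would carry forward an answer given before the diet was tried.

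**How a bias would scale**

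Let *d* be the share of starters who leave early, *f* the share of leavers who still answer, and *a_s* and *a_l* the proportions of stayers and leavers who find the VLED acceptable.

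- Among those who answer: [(1 − d)·a_s + d·f·a_l] / [(1 − d) + d·f]
- Among all who started: (1 − d)·a_s + d·a_l
- Bias = the first minus the second. At f = 0 this reduces to d·(a_s − a_l).

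Every input below is an assumption; the protocol gives none of them. With a_s = 0.85 and a_l = 0.35 (a 50-point difference):

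| d | All starters | Reported, f = 0 | Bias, f = 0 | Reported, f = 0.5 | Bias, f = 0.5 |
|---|---|---|---|---|---|
| 10% | 0.765 + 0.035 = 80% | 85% | 5 points | 0.7825 / 0.95 = 82.4% | 2.4 points |
| 20% | 0.680 + 0.070 = 75% | 85% | 10 points | 0.7150 / 0.90 = 79.4% | 4.4 points |
| 30% | 0.595 + 0.105 = 70% | 85% | 15 points | 0.6475 / 0.85 = 76.2% | 6.2 points |

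A second set of assumed rates shows how far the result depends on the inputs. Take a_s = 0.80, no leaver answering and d of 5%, 10%, 20% and 30%:

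- a_l = 0.20: 3, 6, 12 and 18 points.
- a_l = 0.50: 1.5, 3, 6 and 9 points.
- a_l = 0.80 (leavers rate as stayers do): zero throughout.

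If every leaver answers (f = 1), the bias is zero whatever the rates.

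**The case against.** A reader might infer that everyone who leaves the VLED early is never asked, and that acceptability is therefore overstated as a matter of fact. The protocol does not support either step.

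- **Those who stop the diet are not all lost.** The synopsis continues follow-up after treatment is stopped, and Section 4.3.8 does not restrict the form to people still on the diet. Only those who withdraw from the study before Appt 9 lack any planned post-baseline rating. This stands and narrows the point, although the later answers may come long after the experience.
- **Section 3.5 does not say that weight and HbA1c are the only data kept.** That sentence sets the source and window for the 12-month values. This is correct as a reading. Even so, what continues is data from routine visits, and a study questionnaire would not normally be among them.
- **Information on leavers is recorded.** Intolerance, poor compliance, reasons for early food reintroduction and, on the adverse event form, treatment modified or stopped are all captured. They can be reported beside the scores. They are not participants' own ratings of acceptability, ease of use or value, so they do not replace the outcome measure.
- **Leaving the VLED early need not mean dislike.** Section 4.1.1 moves patients on when BMI falls below a stated level and allows flexible phase lengths. This stands: the direction of any bias is plausible but not established.
- **The figures are assumptions, on a metric the protocol does not use.** Section 4.5.2 lists change in a questionnaire measure, not a percentage finding the diet acceptable. This also stands; the numbers show only how a bias would scale.
- **Handling of missing questionnaires belongs in the SAP.** Agreed, and its absence from the protocol is not criticised here. Whether the answers are requested at all is a protocol matter.

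**Conclusion.** The point holds in a limited form. The protocol plans no attitude rating at the time a participant stops the VLED or withdraws, and anyone who withdraws before Appt 9 has no planned rating based on experience. Acceptability may be overstated if leavers rate the diet lower than stayers and mostly do not answer.

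The size cannot be estimated from the document. The 5 to 15 points rest wholly on 10% to 30% leaving, none of them answering, and a 50-point difference in ratings; the bias roughly halves if half the leavers answer and vanishes if leavers rate as stayers do. This is a cheap improvement to a secondary measure, worth making because missing answers cannot be recovered afterwards. It is not a flaw in the remission endpoint.

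**What to change.** In Section 4.3.8, and in Section 4.6 and Appendix A to match:

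1. Send the existing electronic Food Acceptability Questionnaire when a participant stops the VLED early or withdraws from the study, whatever the week, subject to consent. Add the exit questionnaire to Section 3.5.
2. State that participants who stop the diet but remain in the study are still asked at Appts 9 and 20.
3. Report exit answers separately from the week 13 scores, with the number not answering and their recorded reasons for leaving where known.

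The cost is one added trigger for a form that already exists; no new instrument or visit is needed. Some leavers will not reply, so the gap will be reduced rather than closed. Exit answers will come at varying weeks, which is why they should not be pooled with the week 13 scores.
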